- Study Day: The day before the first dose of the double-blind study drug will be defined as Study Day -1 and the day of the first dose will be defined as Study Day 1.
- Follow-up Day: The day after the last dose of the double-blind study drug will be defined as Follow-up Day 1.
- Treatment Groups: Placebo, Lu AA21004 10 mg, Lu AA21004 20 mg
- MADRS total score: Sum of the 10 MADRS items
- HAM-D17 total score: Sum of the 17 HAM-D items
- HAM-D21 total score: Sum of the 21 HAM-D items
- SDS total score: Sum of the 3 SDS items
- MADRS response: Percentage of subjects whose MADRS total score decreased by a greater than or equal to 50% from baseline
- MADRS remission: Percentage of subjects whose MADRS total score decreased to 10 or less

Definition of TIME WINDOW

For each test/observation/evaluation item, all evaluable data (non-missing and acceptable according to the “Handling Rules for Analysis Data”) will be handled according to the following rules.

For each visit other than Week 8 (LOCF), observation in the corresponding time interval will be used. If more than one observation lies within the same visit window, the observation with the closest Study Day to the scheduled Study Day will be used. If there are two observations equidistant to the scheduled Study Day, the later observation will be used. The difference from the scheduled Study Day will be judged based on the Study Day and Follow-up Day.

For Week 8 (LOCF), the last observation obtained in the corresponding time interval will be used.

MADRS, CGI-S

Visit	Scheduled Study Day (days)	Time Interval (days)	
		Study Day	Follow-up Day
Screening	Study Day: -22	<= -12	-
Placebo lead-in	Study Day: -8	-11 - -5	-
Baseline (Week 0)	Study Day: -1	-4 - 1	-
Week 1	Study Day: 7	2 - 10	<8
Week 2	Study Day: 14	11 - 21	<8
Week 4	Study Day: 28	22 - 35	<8
Week 6	Study Day: 42	36 - 49	<8
Week 8	Study Day: 56	50 <=	<8
Week 8 (LOCF)	-	2 <=	<8

HAM-D

Visit	Scheduled Study Day (days)	Time Interval (days)	
		Study Day	Follow-up Day
Screening	Study Day: -22	<= -12	-
Placebo lead-in	Study Day: -8	-11 - -5	-
Baseline (Week 0)	Study Day: -1	-4 - 1	-
Week 8	Study Day: 56	2 <=	<8
Week 8 (LOCF)	-	2 <=	<8

CGI-I

Visit	Scheduled Study Day (days)	Time Interval (days)	
		Study Day	Follow-up Day
Baseline (Week 0)	Study Day: -1	<= 1	-
Week 1	Study Day: 7	2 - 10	<8
Week 2	Study Day: 14	11 - 21	<8
Week 4	Study Day: 28	22 - 35	<8
Week 6	Study Day: 42	36 - 49	<8
Week 8	Study Day: 56	50 <=	<8
Week 8 (LOCF)	-	2 <=	<8

SDS

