2.1 Primary Endpoint(s) and Analytical Methods

2.1.1 Primary Analysis

Analysis Set: Full Analysis Set

Analysis Variable(s): Change from baseline in the MADRS total score at Week 8 of treatment with double-blind study drug

Analytical Method(s): Primary efficacy analysis will be performed based on a mixed model for repeated measurements (MMRM) analysis of covariance with change from baseline in MADRS total score at each post-dose visit as a dependent variable, and visit, treatment group, visit-by-treatment group interaction, baseline MADRS total score-by-visit interaction as fixed effects.

Comparisons between each Lu AA21004 group and the Placebo group will be performed at Week 8 of treatment with double-blind study drug. For the adjustment of freedom degree, Satterthwaite method will be used. For covariance structure analysis among the subjects, the same, unstructured covariance matrix is assumed.

[Model]

Change from baseline in the MADRS total score = Visit + Treatment group + Treatment group \times Visit + baseline MADRS total score \times Visit

Holm adjustment will be used for multiplicity for the comparison. That is,

$$H_{01}: \mu_{\text{Placebo}} = \mu_{10 \text{ mg}}$$

$$H_{02}: \mu_{\text{Placebo}} = \mu_{20 \text{ mg}}$$

A p-value for each null hypothesis will be set to be P_1 and P_2 . A test will be performed according to the following procedures after setting P_1 and P_2 in an ascending order as $P^{(1)}$ and $P^{(2)}$ and setting the corresponding null hypotheses as $H^{(1)}$ and $H^{(2)}$.

Step 1: In the case of $P^{(1)} > 0.025$, end the test procedures by holding null hypotheses $H^{(1)}$ and $H^{(2)}$. In the case of $P^{(1)} \leq 0.025$, reject null hypothesis $H^{(1)}$ and proceed to Step 2.

Step 2: In the case of $P^{(2)} > 0.05$, hold null hypothesis $H^{(2)}$. In the case of $P^{(2)} \leq 0.05$, reject null hypothesis $H^{(2)}$.

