2.3 Other Analysis/Additional Endpoint(s) and Analytical Methods

Analysis Set: Full Analysis Set

Analysis MADRS total score, MADRS single item

Variable(s): MADRS response, MADRS remission
 HAM-D17 total score, HAM-D single item, HAM-D21 total score
 CGI-I score, CGI-S score, SDS total score, SDS single item
 DSST score, PDQ-5 score, PDQ-5 single item

Visit: [MADRS total score, MADRS single item, CGI-S score]
 Screening, Placebo Lead-in, Baseline, Week 1, Week 2, Week 4, Week 6, Week 8, and Week 8 (LOCF)
 [MADRS response, MADRS remission, CGI-I score]
 Week 1, Week 2, Week 4, Week 6, Week 8, and Week 8 (LOCF)
 [HAM-D17 total score, HAM-D single item, HAM-D21 total score]
 Screening, Placebo Lead-in, Baseline, Week 8, and Week 8 (LOCF)
 [SDS total score, SDS single item]
 Placebo Lead-in, Baseline, Week 8, and Week 8 (LOCF)
 [DSST score, PDQ-5 score, PDQ-5 Single item]
 Placebo Lead-in, Baseline, Week 1, Week 8, and Week 8 (LOCF)

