Analytical Method(s):	
(1) MADRS total score
 
MADRS total score will be analyzed for each visit. Descriptive statistics and two-sided 95% confidence intervals of means will be provided for the observed values and the change from baseline (each post-dose visit - Baseline) in the MADRS total score at each post-dose visit by treatment group. The change from baseline in the MADRS total score at each post-dose visit (dependent variable) will be analyzed using an ANCOVA model with treatment as a fixed effect and the baseline MADRS total score as a covariate. Least Square (LS) means and the two-sided 95% confidence intervals will be provided for each treatment group. The point estimates of the differences in the LS means between each Lu AA21004 group and the placebo group (each Lu AA21004 group - placebo group) and the two-sided 95% confidence intervals will be provided. The differences in the LS means will be tested for treatment differences.
 
(2) MADRS single item
 
MADRS single item will be analyzed for each visit. Descriptive statistics and two-sided 95% confidence intervals of means will be provided for the observed values and the changes from baseline (each post-dose visit - Baseline) in the MADRS single item at each post-dose visit by treatment group. The point estimates of the mean differences in the changes from baseline between each Lu AA21004 group and the placebo group (each Lu AA21004 treatment group – placebo group) and the two-sided 95% confidence intervals will be provided.
 
(3) MADRS response
 
MADRS response will be analyzed for each visit. Frequency distributions will be provided by treatment group along with the point estimates and the two-sided 95% confidence intervals. Odds ratios of each Lu AA21004 group to the placebo group (each Lu AA21004 group / placebo group) and the two-sided 95% confidence intervals will be provided and tested for treatment differences using a logistic regression model. The logistic regression model will include MADRS response as a dependent variable, and treatment group and baseline MADRS total score as independent variables.

-----------------------	--

(4) MADRS remission

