CGI-S score will be analyzed for each visit. Descriptive statistics and two-sided 95% confidence intervals of means will be provided for the observed values and the change from baseline (each post-dose visit - Baseline) in the CGI-S score at each post-dose visit by treatment group. The change from baseline in the CGI-S score will be performed based on a mixed model for repeated measurements (MMRM) analysis of covariance with change from baseline (post-dose visit - Baseline) in the CGI-S score at each post-dose visit (Week 1 to Week 8) as a dependent variable, and visit, treatment group, visit-by-treatment group interaction, baseline CGI-S score-by-visit interaction as fixed effects. Least Square (LS) means and the two-sided 95% confidence intervals at each visit will be provided for each treatment group. The point estimates of the differences in the LS means between each Lu AA21004 group and the placebo group (each Lu AA21004 - placebo group) and the two-sided 95% confidence intervals will be provided. The change from baseline in the CGI-S score at each post-dose visit (dependent variable) will be analyzed using an ANCOVA model with treatment as a fixed effect and the baseline CGI-S score as a covariate. Least Square (LS) means and the two-sided 95% confidence intervals will be provided for each treatment group. The point estimates of the differences in the LS means between each Lu AA21004 group and the placebo group (each Lu AA21004 group - placebo group) and the two-sided 95% confidence intervals will be provided. The differences in the LS means will be tested for treatment differences.

(10) SDS total score

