2.4.2 Handling of Dropouts or Missing Data

Missing test results and data determined to be non-evaluable according to the Handling Rules for Analysis Data will not be used for hypothesis testing and estimations. When individual items are missing from a multiple-item assessment, the total score will be set to missing. (MADRS total score, HAM-D17 total score, HAM-D21 total score, SDS total score, and PDQ-5 score)

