2.4.8 Examination of Subgroups

Analysis Set: Full Analysis Set

Analysis Variable: Change from baseline in the MADRS total score at Week 8 of double-blind

Variable(s): study drug (Week 8 - Baseline)

Stratum: Age (years) [Min<= - <=50, 51<= - <=Max]

Gender [Male, Female]

MADRS Total Score at [Min<= - <=30, 31<= - <=Max]

Baseline

Analytical Method(s): The following summaries will be provided for the above analysis variable(s) for each stratum.

- (1) The same mixed model for repeated measurements (MMRM) analysis of covariance as section “2.1.1 Primary Analysis” will be applied. Least Square (LS) means and the two-sided 95% confidence intervals at each visit will be provided for each treatment group. The point estimates of the differences in the LS means between each Lu AA21004 group and the placebo group (each Lu AA21004 – placebo group) and the two-sided 95% confidence intervals will be provided.

3 Safety Analysis

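### SAP 2.3 (1) gives the MADRS total score only observed-case ANCOVAs at Weeks 1, 2, 4 and 6, although the primary MMRM already models those visits; adding its estimates is nearly free

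*SAP*

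**What the plan says.** **MADRS by visit.** SAP 2.3 (1) states: "The change from baseline in the MADRS total score at each post-dose visit (dependent variable) will be analyzed using an ANCOVA model", with treatment as fixed effect and baseline MADRS as covariate. It asks for LS means, differences from placebo, 95% confidence intervals and a test. The visits are Weeks 1, 2, 4, 6 and 8, plus Week 8 (LOCF).

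**Data used.** The time-window rules state: "For each visit other than Week 8 (LOCF), observation in the corresponding time interval will be used". SAP 2.4.2 adds that missing results, and data judged non-evaluable "according to the Handling Rules for Analysis Data will not be used for hypothesis testing and estimations". Apart from the LOCF row, these are therefore observed-case analyses.

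**Primary model.** The MMRM of 2.1.1 has "change from baseline in MADRS total score at each post-dose visit as a dependent variable", with visit-by-treatment and baseline-by-visit terms and an unstructured covariance. Only one contrast per dose is requested: "Comparisons between each Lu AA21004 group and the Placebo group will be performed at Week 8 of treatment with double-blind study drug".

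**Other scales.** For CGI-S, 2.3 (9) states: "The change from baseline in the CGI-S score will be performed based on a mixed model for repeated measurements (MMRM) analysis of covariance". It asks for LS means and differences at each visit, then repeats the by-visit ANCOVA. CGI-I (8), DSST (12) and PDQ-5 (13) follow the same pattern. HAM-D17 and SDS have one post-dose visit each and get ANCOVA only.

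**Subgroups.** SAP 2.4.8 applies the primary MMRM to MADRS within age, sex and severity strata: "Least Square (LS) means and the two-sided 95% confidence intervals at each visit will be provided for each treatment group".

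**Status.** SAP 2.4.5 treats everything outside the primary analysis as supportive or exploratory.

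**The concern.** Among the total and global scores measured at more than one post-dose visit, the MADRS is the only one without an overall MMRM time course, and it is the primary scale. The SAP gives no reason.

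The two methods need different assumptions about missing data. The observed-case ANCOVA conditions on the baseline score alone. If subjects leave because of how they scored after baseline, and this link differs between arms, those who remain are no longer comparable given baseline, and the estimated difference is biased. The MMRM also uses each subject's earlier post-baseline scores, so it allows for such dropout under missing at random (MAR).

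The protocol gives score-related dropout a plausible route. Section 7.5 lists lack of efficacy as a reason for discontinuation, and 7.5.1 ends participation on a MADRS item 10 threshold or when excluded medication is needed. After the early-termination visit, only safety follow-up remains (9.3.5 and 9.3.6).

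At stake are statements about how the effect develops on the primary scale. The subgroup MMRM results at Weeks 1 to 6 would also have no overall result from the same model to set beside them.

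**Working it through.** **1. The plan's own figure.** The documents give no figure for the time course. The related figure is the power in protocol 13.3: 160 per arm, SD 9.5, two-sided 0.025.

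- SE of a difference = 9.5 × √(2/160) = 1.06.
- Difference 3.5: 3.5/1.062 = 3.295; 3.295 − 2.241 = 1.054; power 85.4% (85.1% by noncentral t). The stated figure of more than 80% is reproduced.
- Difference 3.0: 72.0% for one given dose and 85.8% for at least one dose (correlation 0.5 through the shared placebo arm). This is also more than 80%, as the protocol words it.

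**2. Which visits lack an MMRM estimate.**

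| Analysis | By-visit MMRM | By-visit ANCOVA |
|---|---|---|
| MADRS, full analysis set, Weeks 1, 2, 4, 6 | none listed | yes, with test |
| MADRS, full analysis set, Week 8 | primary analysis, with test | yes, with test |
| CGI-I, CGI-S, DSST, PDQ-5 | estimates and CIs | yes; the test sentence follows it |
| MADRS subgroups | estimates and CIs | none |

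The gap is Weeks 1, 2, 4 and 6.

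**3. Possible size of the bias.** Two simulations compared the per-visit observed-case ANCOVA with the likelihood estimate that an unstructured MMRM gives under monotone dropout. Dropout depended on the last observed score. All inputs except the arm size of 160 (simulation B), the Week 8 SD of 9.5 and the Week 8 difference of 3.0 are assumptions.

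*Simulation A.* Samples were large, to isolate bias. True differences were 0.45, 1.05, 1.95, 2.55 and 3.00 at Weeks 1, 2, 4, 6 and 8. SDs were 4.5, 6.0, 8.0, 9.0 and 9.5, and the correlation between adjacent visits was 0.85. In placebo, the log-odds of dropout rose by 1.0 per SD of the last score; on drug, dropout was unrelated to score. Understatement of the effect by ANCOVA, in MADRS points:

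| Dropout per arm | Week 1 | Week 2 | Week 4 | Week 6 |
|---|---|---|---|---|
| 5% | 0 | 0.06 | 0.15 | 0.24 |
| 10% | 0 | 0.14 | 0.32 | 0.50 |
| 20% | 0 | 0.27 | 0.64 | 0.97 |

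The MMRM estimate stayed within about 0.02 of the truth. At 10% dropout the Week 4 bias is 0.32/1.95 = 16% of the true effect, and the Week 6 bias is 0.50/2.55 = 20%. The Week 6 SE under the assumed SD is 9.0 × √(2/160) = 1.01, so 0.50 is about half a standard error.

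With the same dropout rule in both arms, the ANCOVA bias was at most about 0.05 at any visit, even at 30% dropout. With dropout unrelated to score it was nil.

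*Simulation B.* 160 per arm, visit correlation 0.85, true difference 2.5 at Week 6, dropout 14–16% on placebo and 13.5% on drug. When placebo dropout odds rose by 5–10% per MADRS point and drug dropout was unrelated to score, the Week 6 understatement was 0.23–0.55 points (0.23/2.5 = 9%; 0.55/2.5 = 22%). MMRM bias was 0.03 or less. With the steeper rule in both arms, the ANCOVA bias was 0.08 at Week 6 and 0.12 at Week 8. The MMRM estimate also had a 1–4% smaller sampling SD at Weeks 6 and 8.

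**The case against.** The best case for leaving the SAP as it is has five parts.

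- **The sizes depend on assumptions.** This stands. The documents give no dropout rate or visit correlation, and the bias needs a score–dropout link that differs between arms. The item 10 rule is the same for every arm. With one mechanism throughout, the bias is about 0 to 0.1.
- **The earliest visits are hardly affected.** This largely stands. Bias is nil at Week 1 and 0.14 at Week 2 with 10% dropout, so statements about early onset are little exposed.
- **Early-termination scores fill some gaps.** This stands in part. Protocol 9.3.5 asks for a visit within 7 days of discontinuation, and the windows accept data before Follow-up Day 8. Such a score can fill one nearby window but not the later ones. The simulations did not model it, so they may overstate the bias.
- **The analysis is supportive.** This stands. No objective concerns onset, and the subgroup variable is the Week 8 change, whose overall counterpart is the primary MMRM.
- **A second method is useful.** This stands for Week 8, where the observed-case row is a sensitivity result beside the primary one. At Weeks 1 to 6 there is no MMRM result to compare it with.

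A reader might infer that the SAP shields the lesser scales from this bias and leaves only the MADRS exposed. The text does not support that: all four scales keep the same ANCOVA, with the test sentence attached to it. Nor does it support moving the MADRS tests to the MMRM on the ground that other items already do so. Those items attach no test to the MMRM, and 2.4.8 specifies none.

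**Conclusion.** The point holds as a low-cost improvement. At Weeks 1, 2, 4 and 6 the full-set MADRS difference is estimated and tested only by an observed-case ANCOVA, although a model with a weaker missing-data assumption is already being fitted to those visits.

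If dropout depends on post-baseline scores differently by arm, the ANCOVA differences are biased from about Week 4 onward. With about 10–15% dropout the simulated size is roughly 0.3 points at Week 4 and 0.2–0.55 at Week 6. If the mechanism is the same in both arms it is about 0 to 0.1. The simulated direction was against the drug, because poor responders left placebo. The reverse pattern would favour the drug by the same reasoning, though it was not simulated. The MMRM removes the bias only under MAR.

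A reader might go further and infer that the efficacy conclusion is at risk. It is not: the primary Week 8 comparison comes from the MMRM with Holm adjustment, and nothing here changes it or its type I error.

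**What to change.** In SAP 2.3 (1), add LS means, drug–placebo differences and 95% confidence intervals at Weeks 1, 2, 4 and 6 from the MMRM of 2.1.1. Name these as the main MADRS time course, with the primary result as its Week 8 row. Keep the by-visit ANCOVA as a supportive observed-case analysis, as 2.3 (8), (9), (12) and (13) do.

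The cost is a sentence or two of SAP text and extra output from a model already fitted. No data, sample size or primary test changes. It should be written in before unblinding, because a choice between two MADRS time courses made afterwards would look selective.

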MADRS remission will be analyzed for each visit. Frequency distributions will be provided by treatment group along with the point estimates and the two-sided 95% confidence intervals. Odds ratios of each Lu AA21004 group to the placebo group (each Lu AA21004 group / placebo group) and the two-sided 95% confidence intervals will be provided and tested for treatment differences using a logistic regression model. The logistic regression model will include MADRS remission as a dependent variable, and treatment group and baseline MADRS total score as independent variables.

(5) HAM-D17 total score

HAM-D17 total score will be analyzed for each visit. Descriptive statistics and two-sided 95% confidence intervals of means will be provided for the observed values and the change from baseline (each post-dose visit - Baseline) in the HAM-D17 total score at each post-dose visit by treatment group. The change from baseline in the HAM-D17 total score at each post-dose visit (dependent variable) will be analyzed using an ANCOVA model with treatment as a fixed effect and the baseline HAM-D17 total score as a covariate. Least Square (LS) means and the two-sided 95% confidence intervals will be provided for each treatment group. The point estimates of the differences in the LS means between each Lu AA21004 group and the placebo group (each Lu AA21004 group - placebo group) and the two-sided 95% confidence intervals will be provided. The differences in the LS means will be tested for treatment differences.

(6) HAM-D single item

HAM-D single item will be analyzed for each visit. Descriptive statistics and two-sided 95% confidence intervals of means will be provided for the observed values and the changes from baseline (each post-dose visit - Baseline) in the HAM-D single item at each post-dose visit by treatment group. The point estimates of the mean differences in the changes from baseline between each Lu AA21004 group and the placebo group (each Lu AA21004 treatment group - placebo group) and the two-sided 95% confidence intervals will be provided.

(7) HAM-D21 total score

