HAM-D 21 total score will be analyzed for each visit. Descriptive statistics and two-sided 95% confidence intervals of means will be provided for the observed values and the changes from baseline (each post-dose visit - Baseline) in the HAM-D21 total score at each post-dose visit by treatment group. The point estimates of the mean differences in the changes from baseline between each Lu AA21004 group and the placebo group (each Lu AA21004 treatment group - placebo group) and the two-sided 95% confidence intervals will be provided.

(8) CGI-I score

CGI-I score will be analyzed for each visit. Descriptive statistics and two-sided 95% confidence intervals of means will be provided for the CGI-I score by treatment group. The CGI-I will be performed based on a mixed model for repeated measurements (MMRM) analysis of covariance with CGI-I score at each post-dose visit (Week 1 to Week 8) as a dependent variable, and visit, treatment group, visit-by-treatment group interaction, baseline CGI-S score-by-visit interaction as fixed effects. Least Square (LS) means and the two-sided 95% confidence intervals at each visit will be provided for each treatment group. The point estimates of the differences in the LS means between each Lu AA21004 group and the placebo group (each Lu AA21004 - placebo group) and the two-sided 95% confidence intervals will be provided. The CGI-I score at each post-dose visit (dependent variable) will be analyzed using an ANCOVA model with treatment as a fixed effect and the baseline CGI-S score as a covariate. Least Square (LS) means and the two-sided 95% confidence intervals will be provided for each treatment group. The point estimates of the differences in the LS means between each Lu AA21004 group and the placebo group (each Lu AA21004 group - placebo group) and the two-sided 95% confidence intervals will be provided. The differences in the LS means will be tested for treatment differences.

(9) CGI-S score

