SDS total score will be analyzed for each visit. Descriptive statistics and two-sided 95% confidence intervals of means will be provided for the observed values and the change from baseline (each post-dose visit - Baseline) in the SDS total score at each post-dose visit score by treatment group. The change from baseline in the SDS total score at each post-dose visit (dependent variable) will be analyzed using an ANCOVA model with treatment as a fixed effect and the baseline SDS total score as a covariate. Least Square (LS) means and the two-sided 95% confidence intervals will be provided for each treatment group. The point estimates of the differences in the LS means between each Lu AA21004 group and the placebo group (each Lu AA21004 group - placebo group) and the two-sided 95% confidence intervals will be provided. The differences in the LS means will be tested for treatment differences.

(11) SDS single item

SDS single item will be analyzed for each visit. Descriptive statistics and two-sided 95% confidence intervals of means will be provided for the observed values and the changes from baseline (each post-dose visit - Baseline) in the SDS single item at each post-dose visit by treatment group. The point estimates of the mean differences in the changes from baseline between each Lu AA21004 group and the placebo group (each Lu AA21004 treatment group - placebo group) and the two-sided 95% confidence intervals will be provided.

(12) DSST score

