PDQ-5 score will be analyzed for each visit. Descriptive statistics and two-sided 95% confidence intervals of means will be provided for the observed values and the change from baseline (each post-dose visit - Baseline) in the PDQ-5 score at each post-dose visit by treatment group. The change from baseline in the PDQ-5 score will be performed based on a mixed model for repeated measurements (MMRM) analysis of covariance with change from baseline (post-dose visit - Baseline) in PDQ-5 score at each post-dose visit (Week 1 to Week 8) as a dependent variable, and visit, treatment group, visit-by-treatment group interaction, baseline PDQ-5 score-by-visit interaction as fixed effects. Least Square (LS) means and the two-sided 95% confidence intervals at each visit will be provided for each treatment group. The point estimates of the differences in the LS means between each Lu AA21004 group and the placebo group (each Lu AA21004 – placebo group) and the two-sided 95% confidence intervals will be provided. The change from baseline in the PDQ-5 score at each post-dose visit (dependent variable) will be analyzed using an ANCOVA model with treatment as a fixed effect and the baseline PDQ-5 score as a covariate. Least Square (LS) means and the two-sided 95% confidence intervals will be provided for each treatment group. The point estimates of the differences in the LS means between each Lu AA21004 group and the placebo group (each Lu AA21004 group – placebo group) and the two-sided 95% confidence intervals will be provided. The differences in the LS means will be tested for treatment differences.

(14) PDQ-5 single item

PDQ-5 single item will be analyzed for each visit. Descriptive statistics and two-sided 95% confidence intervals of means will be provided for the observed values and the changes from baseline (each post-dose visit - Baseline) in the PDQ single item at each post-dose visit by treatment group. The point estimates of the mean differences in the changes from baseline between each Lu AA21004 group and the placebo group (each Lu AA21004 treatment group - placebo group) and the two-sided 95% confidence intervals will be provided.

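### SAP 2.3 contrasts HAM-D21 total and the single items as unadjusted mean change, while the corresponding totals use ANCOVA on their own baseline: valid, but usually less precise, and no reason is given

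*SAP*

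**What the plan says.** SAP 2.3 treats two groups of outcomes differently.

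- **Totals.** Entries (1) MADRS, (5) HAM-D17, (10) SDS and (13) PDQ-5 model change from baseline with the outcome's own baseline in the model. For HAM-D17 the change is analysed "using an ANCOVA model with treatment as a fixed effect and the baseline HAM-D17 total score as a covariate". LS means, LS mean differences from placebo, 95% intervals and a test follow.
- **Single items and HAM-D21.** Entry (2) summarises "changes from baseline (each post-dose visit - Baseline) in the MADRS single item at each post-dose visit by treatment group", entry (6) "changes from baseline (each post-dose visit - Baseline) in the HAM-D single item at each post-dose visit by treatment group" and entry (11) "changes from baseline (each post-dose visit - Baseline) in the SDS single item at each post-dose visit by treatment group". Entries (7) HAM-D21 and (14) PDQ-5 items follow the same pattern. The between-group result in all five is "The point estimates of the mean differences in the changes from baseline between each Lu AA21004 group and the placebo group" with 95% intervals. No model, covariate, LS mean or test is named.

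Baseline is a listed visit for every one of these variables. SAP 2.4.1 records that no further covariates will be added after blind data review. It does not say why a variable's own baseline is used for totals but not here. SAP 2.4.5 classes everything beyond the primary analysis as supportive or exploratory.

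**The concern.** A change score subtracts each subject's baseline in full, which amounts to assuming that follow-up rises one point for each baseline point. ANCOVA estimates that slope. When the true slope differs from 1, the raw contrast has more residual variance than the adjusted one, and part of a chance difference in baseline means remains in the estimate.

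The entry thresholds in Protocol 7.1 apply to MADRS total, HAM-D17 and CGI-S. Single items are not restricted in that way, apart from MADRS item 10, which exclusion criterion 10 keeps below 5. Item baselines can therefore be widely spread relative to follow-up, and that is where estimating the slope helps most.

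There is also a consistency problem. HAM-D17 and HAM-D21 come from the same assessment and share 17 items, but would be reported with different estimators. A discrepancy between them could not be put down cleanly to the four extra items.

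What is at stake is the precision and comparability of the symptom-level description.

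**Working it through.** **The plan's own figure.** The documents give no figure for these outcomes. The only power statement is for MADRS total (Protocol 13.3: 160 per group, SD 9.5, two-sided 0.025). SE = 9.5 × √(2/160) = 1.062. For a difference of 3.5, power is Φ(3.5/1.062 − 2.241) = 85.4%. For at least one dose at a difference of 3.0 it is 85.8%, taking correlation 0.5 from the shared placebo arm. Both agree with the stated figure of more than 80%, and neither depends on the point made here.

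**Formulas.** Let k be follow-up SD divided by baseline SD and ρ their correlation, both common to the arms. The slope is ρk. In units of baseline variance:

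- raw change: k² + 1 − 2ρk
- ANCOVA residual: k²(1 − ρ²)
- raw minus ANCOVA: (1 − ρk)², which is never negative and is zero only at slope 1.

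Adjusted interval width divided by raw width is the square root of the variance ratio. A baseline mean difference of one unit shifts the raw estimate by ρk − 1, so the fraction carried is 1 − slope. Its sign is reversed when the slope is below 1.

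**Reduction in interval width from adjustment (k and ρ assumed).**

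| k | ρ = 0.2 | ρ = 0.3 | ρ = 0.5 | ρ = 0.8 |
|---|---|---|---|---|
| 1 | 22.5% | 19.4% | 13.4% | 5.1% |
| 1.25 | 14.7% | 11.4% | 5.5% | 0.0% |
| 1.5 | 9.7% | 6.7% | 1.8% | 2.4% |
| 2 | 4.4% | 2.1% | 0.0% | 10.6% |

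Example: at k = 1 and ρ = 0.5 the variances are 1 and 0.75, and 1 − √0.75 = 13.4%. The two zeros are cases where ρk = 1.

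The shift per unit of baseline imbalance is −0.50 at k = 1, ρ = 0.5; −0.55 at k = 1.5, ρ = 0.3; and 0 at k = 2, ρ = 0.5.

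**HAM-D21.** The entry threshold on HAM-D17 narrows the baseline, so assume SD 4 at baseline and 7 at Week 8. The variance ratio is 49(1 − ρ²)/(65 − 56ρ).

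- ρ = 0.2: 47.04/53.8 = 0.874, so 6.5% narrower
- ρ = 0.3: 44.59/48.2 = 0.925, so 3.8% narrower
- ρ = 0.5: 36.75/37 = 0.993, so 0.3% narrower

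**Simulation check** (4,000 two-arm trials per setting, 160 per arm).

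| k, ρ | Raw/adjusted width | Correlation with baseline imbalance, raw | Same, adjusted |
|---|---|---|---|
| 1, 0.5 | 1.154 | −0.49 | 0.01 |
| 1.5, 0.3 | 1.070 | −0.38 | −0.02 |
| 2, 0.5 (slope 1) | 0.998 | 0.01 | 0.01 |

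In the first setting the raw estimates had an empirical SD of 0.1115, against a theoretical SE of √(1 × 2/160) = 0.1118. The raw standard error is therefore correct; it is simply larger than the adjusted one.

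**The case against.** The strongest reply is that this is untested descriptive output. The five entries sit under additional endpoints, none is a protocol endpoint, and the SAP keeps tests for the totals. Observed baseline values are summarised by arm, so an item-level imbalance would be visible. All of this stands and sets the priority low. It does not explain why the less precise contrast was chosen when the better one is specified in adjacent entries.

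Four stronger readings are tempting and are not supported:

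- **That the plan ignores baseline.** It does not. Subtracting baseline is an adjustment with the slope fixed at 1, and only the fraction (1 − slope) of an imbalance is carried.
- **That regression to the mean, floor effects or chance imbalance create false item-level effects.** Under randomisation these act equally on the arms in expectation, and the raw interval already includes that sampling variation. Results that arise by chance across many items are a multiplicity matter, which ANCOVA does not remove.
- **That power is lost.** No test is planned for these outcomes.
- **That many visits are involved throughout.** There are four item families plus one total. MADRS items have five post-baseline visits, PDQ-5 items have Weeks 1 and 8, and HAM-D and SDS have Week 8 only (each also has LOCF).

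One technical reservation has some force. Some HAM-D items are scored only 0 to 2 (Protocol 9.1.8.1), so a linear covariate is approximate. The raw change also imposes a straight line, with its slope fixed, so this does not favour it.

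**Conclusion.** The point holds as a low-priority improvement in precision and consistency. The raw contrasts are valid with nominal coverage. In large samples the adjusted contrast is never less precise, and the two are equal only at slope 1. There the raw interval may even be marginally narrower in a finite sample (ratio 0.998 in the simulation).

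The size of the gain cannot be taken from the documents. Over k from 1 to 2 and ρ from 0.2 to 0.8 the adjusted interval is 0% to 22.5% narrower. For HAM-D21, under the assumed SDs, the gain is 0.3% to 6.5%. These ranges are illustrations, not bounds: if an item's SD fell during treatment (k = 0.8), the gain would be 20.0% to 31.8% over the same ρ. All figures assume a common slope and common variances across arms.

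A reader might infer that the main efficacy conclusions are affected. They are not. The primary MMRM, the secondary ANCOVA and logistic models, the Holm procedure, the significance level and the sample size do not depend on these entries.

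**What to change.** In SAP 2.3 (2), (6), (7), (11) and (14), replace the raw difference in mean change with ANCOVA of change from baseline, with treatment as fixed effect and the same item's (or HAM-D21's) baseline score as covariate. Report LS means, LS mean differences from placebo and 95% intervals at the visits already listed. Keep the descriptive statistics, and add no tests. If the raw contrasts are kept instead, label them as unadjusted so that HAM-D21 and the items are not read alongside the adjusted totals as like for like.

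The cost is a change of SAP wording, made before unblinding, and reuse of the existing ANCOVA program. No new data, subjects or procedures are needed, since the baseline scores are already collected at Visit 3.
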